5.2.2.3. Well to Sick Analysis

For continuous endpoints during well to sick, i.e. after first occurrence of new or increased symptoms in participants based on Electronic diary (defined in [Section 5.2.2.1](#)), the change from baseline will be summarized descriptively by day, defining the first occurrence of new or increased symptoms based on Electronic diary as day=1. For the purpose of the well to sick analysis, the baseline is defined as the average of the endpoint values during the 7-day period before the first occurrence of new or increased symptoms. If a participant has no data during these 7 days, the average of the endpoint values for the closest 3 available days prior to these 7 days will be used for the baseline.

The disease progression from well to sick will be modelled monotonically using data only up to the time before recovery, so that the potential recovery phase afterwards is excluded. The time before recovery is defined in [Section 5.2.2.2](#).

To categorize the well to sick progression during this period (from day=1 to the time before recovery), for each endpoint, the change from baseline will be summarized as follows:

- a. The number and percentage of participants who have less than two days of available data for the endpoint during this period.
- b. For each participant who has two or more days of available data for the endpoint during this period, a linear regression of the change from baseline vs. day, without intercept, will be fit. The participants without a statistically significant trend from the model will be categorized as non-responder, and number/percentage will be summarized.
- c. For each participant with a statistically significant trend from the model in b, two measures will be computed: the day at which the first maximum change from baseline value (direction determined by linear fit in b) is reached during the period (defined as Tmax), and the ratio of the maximum change to the Tmax (defined as Growth Rate). The descriptive summary of the two measures for these significantly responding participants will be presented.

In addition, the well to sick progression period for each endpoint will be modelled monotonically. Firstly, a linear mixed effect model for the change from baseline vs. day will be used, with slope (i.e. without intercept) included as both fixed effects and random effects (to account for participant level variation). The number of participants used by the model, estimate of the slope's fixed effect mean, standard error, 90% CI, and p-value, as well as the variance estimate for its random effect will be presented.

Secondly, for the statistically significant endpoints determined by the linear mixed effect model, a logistic sigmoid growth/Emax model will also be considered for the population model:

$$y_{ij} - a_{i0} = \frac{d - a_{i0}}{1 + \left(\frac{\text{day}_j}{c}\right)^{-b}} + \varepsilon_{ij}$$

where i represents the i th participant, j represents the j th day, a_{i0} is the baseline value for the i th participant, and y_{ij} is the continuous endpoint value modelled as response. Parameters b , c , d represent the Hill slope, the day at which 50% effect is reached, and the asymptotic maximum sick response for the model, respectively, which can have participant level variation.

To facilitate model convergence, the maximum value observed during the period for each participant (direction determined by individual linear fit from b above), \max_i , will be used to substitute parameter d , and a linear mixed effect model of the logit transformed $\log((\max_i - y_{ij})/(y_{ij} - a_{i0}))$ vs $\log(\text{day})$ will be used for the longitudinal changes, with its intercept and slope included as both fixed effects and random effects. The number of participants used by the model, estimates of the fixed effect means, standard errors, 90% CIs, and p-values, as well as the variance estimates for their random effects will be presented. The

back-transformed mean estimates and 90% CIs for the parameters b and c , where $b = -\text{slope}$ and $c = \exp(-\text{intercept/slope})$, will also be presented.

Additional models may also be considered as appropriate, and the models' goodness of fit will be assessed using Akaike/Bayesian information criteria.

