9.2. Sample Size Determination

The sample size determination is based on the primary study objective, which is to obtain data to characterize the relationship between symptoms and voice features for acute viral respiratory illness for RT-PCR confirmed SARS-CoV-2, influenza virus, or RSV positive participants as they progress from well to sick states.

For this exploratory study, it is planned to obtain a total of 100 completers who are RT-PCR confirmed negative to SARS-CoV-2, influenza virus and RSV RT-PCR (at swab #1), and SARS-CoV-2, influenza or RSV RT-PCR confirmed positive (at swab #2) reporting new or increased symptoms.

it is estimated that approximately 5500 participants (8700 in total including participants that have been enrolled prior to protocol amendment #1) will be needed to be enrolled in the study.

A reassessment of study feasibility and enrollment requirements is anticipated, including the required sample size, after infection rates and compliance data from the first 1000 completers analyzed.

The case definition that will be used to define cases for the primary objective of the study will be as follows:

Negative RT-PCR at swab #1 and Positive RT-PCR at swab #2 who develop 1 or more new or increased symptoms from baseline from the following list:

Fever, chills, rigors, myalgia, headache, fatigue, sore throat, rhinorrhea, congestion, vomiting, nausea, diarrhea, new olfactory and taste disorder(s), cough, wheezing, shortness of breath, or difficulty breathing.

Depending on the distribution of the 3 viruses, this sample size may be adequate to build general algorithm(s) for early detection of upper respiratory illnesses. This sample size will allow identification of any additional data required to finalize this algorithm(s).

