2.2. Study Design

This is a low-interventional, observational study with planned enrollment of approximately 8,700 participants 18 years of age or older in order to collect a total N=100 participants with (1) RT-PCR confirmed negative SARS-CoV-2, influenza virus and RSV (swab #1) and (2) RT-PCR confirmed positive SARS-CoV-2, influenza virus and RSV (swab #2 or any subsequent swab) symptomatic completers.

Each participant will be required to stay in the study for 6 weeks. If the participant tests positive for any of the three viruses at swab #1 or swab #2, they will continue the study until the end of Week 8.

[figure not shown]
Participants will record acute respiratory illnesses and SARS-CoV-2 symptoms and voice data daily for up to a maximum of 8 weeks in both the well state and, should they become ill, the sick state, utilizing the Electronic diary on their Mobile application. Once enrolled, the participant will start recording symptoms and voice in the Electronic diary, with daily time commitment to this portion of the study expected to be 2-4 minutes. Two nasal self-swab collection kits will be ordered for delivery to the participant once they are enrolled in the study. The participant will be asked to self-swab when the test kit arrives (swab #1). The kit, including the specimen, will be returned to the central lab for RT-PCR SARS-CoV2/Influenza/RSV RT-PCR testing. The participant is expected to complete 3 phonemes and 5 lines of reading each day, in addition to score the self-reported symptoms in the Electronic diary. If participants become sick (self-report) with new or increased symptoms of respiratory illness, they will be asked to self-swab (swab #2) and return the sample for central SARS-CoV-2/Influenza/RSV RT-PCR testing. If the participant does not develop any

new or increased symptoms between swab #1 and end of Week 6, they will obtain a self-swab (swab #2) at Day 42.

If the participant tests positive for any of the three viruses at swab #1 or swab #2, they will continue the study until end of week 8. If they test negative for the three viruses at swab #1 and swab #2, they will exit the study at approximately the end of week 6 when the test results are returned. The results of the RT-PCR testing will be shared with participants.

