5.2. General Methods

Data will be summarized using descriptive statistics (number of participants (n), mean, median, standard deviation (SD), minimum and maximum, as appropriate) for continuous (or near continuous) variables, and using frequency and percentages for discrete variables.

Participants can complete the Electronic diary multiple times per day, and each time is considered a session. The session with the most compliant voice and symptom data, and the highest quality voice data will be used for that day to compute the summary statistics. All individual sessions will be used for statistical modeling.

P-values will be generated where appropriate and any p-value < 0.10 will be considered statistically significant. Due to the exploratory nature of the study, p-values will not be adjusted for multiplicity. P-values will be rounded to 3 decimal places and therefore presented as 0.xxx; P-values smaller than 0.001 will be reported as '<0.001'.

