6.1.1. Main Analysis

6.1.1.1. Well to Sick

- Estimator: Primary Estimator E1(Section 2.1.1). This estimator is intended to provide a population level estimate of the well state as well as changes in symptoms and voice features from well to sick in symptomatic SARS-CoV-2, influenza virus, or RSV positive participants using Electronic diary.
- Analysis Sets: (a) Participants in Primary Analysis Set (Section 4) who become SARS-CoV-2, influenza virus or RSV positive (at Swab#2) and symptomatic during the study; (b) A subset of (a) who are symptom free at enrollment; (c) A subset of (a) who have symptoms due to chronic pre-existing conditions at enrollment. These analysis sets will be considered as deemed appropriate by data.
- Intercurrent events and missing data: (a) There are no particular intercurrent events considered. Participants who have events that lead to missing data will be included and missing data will not be imputed. (b) Inadequate compliance – data will be used as recorded.
- Statistical Method: Summary statistics and linear mixed effect analyses as described in Section 5.2.2.3. The total symptom score, each symptom and each voice feature will be modelled individually.
- Summaries:
 - a. Descriptive summaries and corresponding plots of the mean/SD will be provided. For linear mixed effect model analyses, estimates for all parameters fixed effect means, standard errors, 90% CIs, and p-values, as well as the variance estimates for their

random effects will be provided (as described in [Section 5.2.2.3](#)). Results from all models will be presented in a table.

- b. To assess the well-to-sick analysis baseline: For voice features that are determined as statistically significant based on linear model mixed effect analysis, the difference of the voice feature values between every pre-symptomatic day (starting from enrollment day) and the well-to-sick baseline (i.e. 7-day average before symptomatic onset as described in [Section 5.2.2.3](#)) will be computed. The mean/SD of the differences across participants in the analysis set will be plotted by day up to the symptomatic onset.

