If the total symptom remains below 40% of the maximum total symptom score after swab #2, the end of the window will be the swab #2 day.

The **well state** is defined by considering a window of Electronic Diary data around a negative RT-PCR test at swab #1, from 8 days before swab #1 up to 14 days before a positive swab #2. If there are less than 14 days between swab #1 and swab #2, the well state window ends on the day of swab #1.

For Secondary Analysis Set A

The **well state** is defined by considering an:

- Analysis time window from 8 days before swab #1 up to 8 days after swab #1.
- Analysis time window of 8 days up to and including swab #2.

For Secondary Analysis Set B

The **sick state** is defined by considering an analysis time window of 3 days before and 3 days after swab #1, including swab #1 day.

CCI

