4.2.5. Classical Machine Learning

Using the reduced feature set from Section 4.2.3., classical machine learning algorithms will be trained to perform the binary classification of well versus sick states. Ensemble learning algorithms are the preferred method because they: typically generalize well, are very robust to overfitting, can be trained efficiently, require little hyper-parameter tuning to achieve competitive results, perform predictions quickly and can be easily packaged for deployment²⁰. The classical machine learning approach also lends itself to making understandable predictions. SHapley Additive exPlanations (SHAP)²¹ will be used to investigate the most successful models to determine to what degree each feature influences model output. The main classical machine learning models of interest include: Random Forest²²; Bagging²³; Extreme Gradient Boosting (XGBoost)²⁴; Light Gradient Boosting Machine (LGBM)²⁵; Support Vector Machine (SVM) Ensemble²⁶.

Additional modeling may include a combination of spectrograms (described in Section 4.2.4.) and voice features described in Section 4.2.2. The spectrogram averaged across time may be combined with the voice features and used as the input to the classical machine learning model. In early fusion, a classifier is trained on the combined set of voice features and averaged spectrograms. In late fusion, separate models are trained on averaged spectrograms and voice features, and the final prediction is the average of the output from the two models²⁷⁻²⁹.

In addition, covariance approach which quantifies the linear relationship between features will also be explored to perform the binary classification of well versus sick states. This

approach has been shown to be invariant to the linear transformation of the features³⁰. This invariance property might diminish the intersubject variability of the acoustic features and can also reduce any learning effects of the acoustic features over time on the model performance. The input data for this approach will be the MFCCs matrix, as described in [Section 4.2.4](#).

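### The well-to-sick slope for voice features is fitted in cases only, with no comparison group, so drift or learning in daily recordings cannot be separated from illness change

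*SAP*

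**What the plan says.** SAP 5.2.2.3 sets day 1 at the first new or increased symptoms and takes as baseline the mean of the preceding 7 days. It then fits "a linear mixed effect model for the change from baseline vs. day will be used, with slope (i.e. without intercept", using data up to recovery and a random slope for participant. SAP 6.1.1.1 applies this to each voice feature in initially negative participants who turn positive at swab #2 and become symptomatic. Under SAP 5.2, "any p-value < 0.10 will be considered statistically significant", and "p-values will not be adjusted for multiplicity". Significant endpoints go on to the sigmoid model, and the univariate results help guide feature choice in the algorithm appendix (4.2.3).

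Three places touch on change over time in the recordings:

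- SAP 6.1.1.1(b) plots "the difference of the voice feature values between every pre-symptomatic day (starting from enrollment day) and the well-to-sick baseline", for cases only and only for features already found significant.
- SAP 5.2.2.4 models the well state with day as a random effect, which yields a variance and not a trend.
- Appendix A 4.2.5 says of the covariance approach that it "can also reduce any learning effects of the acoustic features over time on the model performance". The plan therefore recognises that learning may occur.

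**The concern.** The hypothesis to be tested (Protocol 9.1, SAP 5.1) is that voice changes with acute viral illness. Each participant repeats the same phonemes and reading passage daily for 6 to 8 weeks, and the extracted features include speaking rate, pauses and maximum phonation time, which repetition could plausibly alter. Baseline always precedes the sick days, so any such trend has the same form as an illness effect in this model. A significant slope would then show that the feature changed with time around onset, not that illness changed it. Protocol 4.1 says changes will be stratified by test result, but the visible subset analyses (SAP 6.4) split by virus and by age/gender and never set positives against negatives.

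**Working it through.** **The plan's own figures.** No power or precision is stated for the well-to-sick slope. The figures tied to 100 cases concern algorithm sensitivity (Appendix A 4.1), and they reproduce: 1.96 × √(0.7 × 0.3/100) = 8.98%, and 1.96² × 0.21/0.1² = 80.7, so 81 cases.

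**Inputs from the documents.** Cases: "it is planned to obtain a total of 100 completers who are RT-PCR confirmed negative" at swab #1 and positive with symptoms at swab #2 (Protocol 9.2). Enrolment: "planned enrollment of approximately 8,700 participants 18 years of age or older in order to collect a total N=100 participants" (SAP 2.2). Level: 0.10, taken as two-sided because 90% CIs are reported. Baseline: the 7 days before onset, that is days −6 to 0, centred at day −3.

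**Assumptions not in the documents.** Drift size in units of within-person day-to-day SD, length of the sick period T, and the error structure.

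**Step 1: how drift enters the slope.** With drift d per day and no illness effect, the expected change from baseline on day t is d(t + 3). The no-intercept slope is Σt·d(t + 3)/Σt² = d[1 + 9/(2T + 1)]. This gives 2.29d at T = 3, 1.69d at T = 6 and 1.43d at T = 10.

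**Step 2: chance of a significant slope with no illness effect, T = 6.** Here Σt = 21 and Σt² = 91. With independent errors of SD 1, the variance of one participant's slope is (91 + 21²/7)/91² = 154/8281 = 0.0186. The standard error over 100 cases is √(0.0186/100) = 0.0136. At d = 0.02 the expected slope is 0.0338, so z = 2.48 against a critical value of 1.645, and the rejection rate is about 80%. Simulation gives 79%.

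| Assumed drift (SD/day) | Over 42 days | Independent errors | AR(1) 0.5, random-slope SD 0.1 |
|---|---|---|---|
| 0 | 0 | 10% | 10% |
| 0.01 | 0.42 SD | 34% | 19% |
| 0.02 | 0.84 SD | 79% | 44% |
| 0.03 | 1.26 SD | 98% | 73% |

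**Step 3: learning that plateaus.** The assumptions are a time constant of 7 days, onset uniform over study days 4 to 42 and T of 3 to 10 days. Rejection is 14%, 24% and 59% for a total shift of 0.25, 0.5 and 1 SD. For the 0.5 SD shift with T = 6, rejection is about 11% when onset falls on study day 15 or later, so most of the bias comes from early onsets.

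**Step 4: with matched controls.** This used 400 simulated trials per scenario, four controls per case on the same study day, the same model with a group-by-day term, T of 3 to 10 days and random-slope SD 0.02. Rejection with no illness effect is 7% to 13% in every drift and learning scenario. The slope's standard error rises from 0.0119 to 0.0133 (ratio 1.12).

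**The case against.** **No drift size is given.** This stands. With no drift the planned test keeps its level, and unabated linear drift is less plausible than learning that levels off. The 7-day local baseline then removes most of the effect for late onsets. Onset can, however, be as early as the fourth day with symptom data (SAP 5.2.2.1).

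**The relationship analysis is protected.** SAP 5.2.2.5 fits day as a categorical effect, which absorbs drift common to participants by day since onset. That stands for the symptom–voice model, but it does nothing for the slope in 5.2.2.3.

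**Drift would be seen.** The 6.1.1.1(b) plot runs from enrolment and might show it, and the classifiers are tested on negatives. Neither alters the slope, its interval or its p-value.

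**The appendix.** A reader might infer that the classifiers can learn time in study unchecked, since a case's well window runs "from 8 days before swab #1 up to 14 days before a positive swab #2" and precedes the sick window. The documents do not support that reading. Appendix A 3 and 4.4 define a late well window, ending at swab #2, for participants negative at both swabs. Sections 4.6 and 5.5.1 test the best models on them, and 5.5.2 tests the models other than change-from-baseline on participants already positive at swab #1.

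**Context.** The study is exploratory, makes no decision rules and does not adjust p-values. Some exploratory sections are redacted, so a comparison with negatives there cannot be excluded.

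**Conclusion.** The point holds for the visible well-to-sick slope model for voice features. As specified, it cannot tell a time trend from an illness effect, and the no-intercept form enlarges any drift, by about 1.7 times at 6 days. How much this matters depends on a drift that the documents do not quantify. Drift of 0.02 within-person SD per day would make a feature unaffected by illness significant in about 44% to 79% of trials, depending on the error structure. With plateauing learning and late onset the excess is small. It does not follow that the voice findings will be false, or that the algorithm work lacks a check on time in study. In an exploratory study this should be addressed, but it does not invalidate the plan.

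**What to change.** Pre-specify a supportive analysis in SAP 6.1.2 for each voice feature. Take participants negative at both swabs who have no new or increased symptoms in the window. Match them to each case on study day of onset and on the age/sex group of SAP 3.4, and assign a pseudo-onset on that day. Build baseline and window length as for the matched case. Fit the 5.2.2.3 model to both groups with a group-by-day term, and report the case-minus-control slope with its 90% CI beside the planned slope. Secondary Analysis Set A should not be used unchanged, because it includes negatives whatever their symptoms; other respiratory illness among them could shrink the contrast.

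No new data are needed. The number of usable negatives is not stated, but if only 25% of 8,700 had usable results at both swabs, 0.25 × 8,700 − 100 = 2,075 would remain before the symptom restriction, against 400 needed for four per case. The costs are matching choices to state in advance and a standard error about 12% larger. By normal approximation, power for a true slope of 0.03 SD per day falls from about 81% to 73% under the assumptions of step 4. The appendix needs no change on this account.

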4. STUDY DESIGN

4.1. Overall Design

This is a low-interventional, observational study with planned enrollment of approximately 8700 participants 18 years of age or older in order to collect a total N=100 participants with (1) RT-PCR confirmed negative SARS-CoV-2, influenza virus and RSV (swab #1) and (2) RT-PCR confirmed positive SARS-CoV-2, influenza virus and RSV (swab #2 or any subsequent swab) symptomatic completers.

Each subject will be required to stay in the study for 6 weeks. If the participant tests positive for any of the three viruses at swab #1 or swab #2, they will continue the study until the end of Week 8.

Participants will record acute respiratory illness symptoms and voice data daily for up to a maximum of 8 weeks in both the well state and, should they become ill, the sick state, utilizing the Electronic diary on their Mobile application. Once enrolled, the participant will start recording symptoms and voice in the Electronic diary, with daily time commitment to this

portion of the study expected to be 2-4 minutes. Two nasal self-swab collection kits will be ordered for delivery to the participant once they are enrolled in the study. The participant will be asked to self-swab when the test kit arrives (swab #1). The kit, including the specimen, will be returned to the central lab for RT-PCR SARS-CoV2/influenza virus/RSV RT-PCR testing. The participant is expected to complete 3 phonemes and 5 lines of reading each day, in addition to score the self-reported symptoms in the Electronic diary. If participants become sick (self-report) with new or increased symptoms of respiratory illness, they will be asked to self-swab (swab #2) and return the sample for central SARS-CoV-2/influenza virus/RSV RT-PCR testing. If the participant does not develop any new or increased symptoms between swab #1 and end of Week 6, they will obtain a self-swab (swab #2) at Day 42.

If the participant tests positive for any of the three viruses at swab #1 or swab #2, they will continue the study until end of week 8. If they test negative for the three viruses at swab #1 and swab #2, they will exit the study at approximately the end of week 6 when the test results are returned. The results of the RT-PCR testing will be shared with participants.

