5.2.2.2. Definition of Recovery Phase

To define the recovery phase for each participant who has new or increased symptoms (as defined in [Section 5.2.2.1](#)), firstly the maximal total symptom score on or after the first occurrence of new or increased symptoms, as well as the first day on which this maximal total symptom score is reached (defined as the Maximal Score Day), are identified.

Then the beginning of recovery is defined as the first day after the Maximal Score Day when the total symptom score is decreased from the previous day with available symptom data, followed by two more days of non-increasing total symptom scores.

When no beginning of recovery is observed, all days up to the final study day of the participant are considered as before recovery.

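### The population well-to-sick slope is fitted without an intercept, so it mixes onset shift, later progression and window length and is not a rate of progression

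*SAP*

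**What the plan says.** SAP 6.1.1.1 names summary statistics and linear mixed effect analyses as the main method for the primary endpoints. They are applied one at a time to the total symptom score, each symptom and each voice feature. The details are in SAP 5.2.2.3:

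- **Model.** The first population model regresses change from baseline on day. Its time term enters "with slope (i.e. without intercept) included as both fixed effects and random effects".
- **Time axis.** Days are counted by "defining the first occurrence of new or increased symptoms based on Electronic diary as day=1".
- **Response.** Change from baseline, where "the baseline is defined as the average of the endpoint values during the 7-day period before the first occurrence of new or increased symptoms".
- **Window.** Data run from day 1 to before recovery. SAP 5.2.2.2 dates recovery from the total symptom score alone. The starting point is "the first day after the Maximal Score Day when the total symptom score is decreased from the previous day"; days without symptom entries are skipped, and the next two days must not show an increase. If no recovery is seen, "all days up to the final study day of the participant are considered as before recovery". The diary runs "daily for up to a maximum of 8 weeks" (protocol 4.1).
- **Reporting.** "For linear mixed effect model analyses, estimates for all parameters fixed effect means, standard errors, 90% CIs, and p-values" (SAP 6.1.1.1).
- **Gate.** Only endpoints significant on this slope, at p<0.10, go on to the sigmoid/Emax model.

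The separate participant-level regression in item (b) of SAP 5.2.2.3 also has no intercept. No model with an intercept is pre-specified for the linear well-to-sick analysis. Additional models, compared by AIC/BIC, are optional. The one sensitivity analysis (SAP 6.1.2) concerns compliance, not model shape.

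**The concern.** With onset at day 1 and no intercept, the line must be zero at day 0. A feature that moves on the onset day and then stops moving has no place in this model except as a slope. The reported number then depends on how long the window lasts as well as on what happened to the feature.

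Such shapes can arise under the SAP's own rules. The window is cut by the symptom curve, so a voice feature may flatten or fall back inside it. For the total symptom score, the onset rule in SAP 5.2.2.1 guarantees a positive day-1 change.

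Three things are at stake: the meaning of the main primary-endpoint estimate, any reading of it across viruses under SAP 6.4, and the choice of endpoints for the sigmoid step. The algorithm development SAP (4.2.3) also draws on this univariate analysis to guide feature work.

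**Working it through.** The plan states no effect size, SD or expected slope for this model, so there is no figure to reproduce.

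**Closed form.** For one participant observed on days 1 to T, the no-intercept slope is Σ(t·y)/Σ(t²), with Σt = T(T+1)/2 and Σt² = T(T+1)(2T+1)/6.

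- Flat shift c: slope = c·Σt/Σt² = 3c/(2T+1). At T = 7 this is 28c/140 = 0.20c.
- Linear fall from c on day 1 to 0 on day T, y = c(T−t)/(T−1): Σ(t·y) = c·T(T+1)/6, so slope = +c/(2T+1). The ordinary slope with an intercept is −c/(T−1).

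| T | Flat shift: no-intercept slope | Flat shift: true slope | Fall to zero: no-intercept slope | Fall to zero: true slope |
|---|---|---|---|---|
| 3 | 0.43c | 0 | +0.143c | −0.50c |
| 7 | 0.20c | 0 | +0.067c | −0.167c |
| 14 | 0.10c | 0 | +0.034c | −0.077c |
| 28 | 0.053c | 0 | +0.018c | −0.037c |

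At T = 15 the flat-shift slope is 3c/31 = 0.10c. The same flat shift gives slopes (2·28+1)/(2·2+1) = 57/5 = 11.4 times apart between T = 2 and T = 28. Two virus groups with the same flat shift and windows of 5 and 10 days would show 3c/11 = 0.27c and 3c/21 = 0.14c per day.

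**Total symptom score.** Under SAP 5.2.2.1, onset is the first day after the initial three on which the score exceeds the maximum of those three. Every earlier day is at or below that maximum, so the baseline average is too, and the day-1 change must be positive. A line through zero at day 0 fits this only if the change on day t is about t times the change on day 1. That requires change to build up steadily, whereas the onset rule selects a jump.

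**Simulation.** Assumed, not in the documents: 100 participants (the planned number of cases), residual SD 1, 7-day baseline measured with error, between-participant SD of the shift 0.5, T = 2 + Poisson, 400 data sets per scenario, REML, two-sided test at 0.10. The intercept model has fixed and random intercept and slope.

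| Scenario (mean T) | SAP slope | SAP p<0.10 | Intercept model: onset change; slope | Its slope p<0.10 |
|---|---|---|---|---|
| No mean change (7) | 0.000 | 9.8% | 0.01; 0.000 | 11.7% |
| Flat 0.5 SD (4) | 0.159 | 100% | 0.51; −0.002 | 9.5% |
| Flat 0.5 SD (7) | 0.098 | 100% | 0.51; 0.000 | 11.7% |
| Flat 0.5 SD (14) | 0.052 | 100% | 0.51; 0.000 | 9.5% |
| 0.5 SD, linear fall to zero (7) | +0.031 | 87.7% | 0.52; −0.063 | 96.8% |
| 0.3 SD, linear fall to zero (7) | +0.019 | 54.0% | 0.31; −0.038 | 71.8% |
| 0.5 SD, exponential fall 0.3/day (14) | +0.007 | 40.3% | 0.36; −0.028 | 99.0% |
| Linear growth from zero (7) | +0.070 | 100% | 0.06; +0.057 | 93.8% |

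In all three falling scenarios every significant SAP slope was positive, and the intercept model never gave a significant positive slope.

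**Gate.** The last column tests the post-onset slope only, which is a different null from no change at all. The like-for-like comparison is with the joint 2-df test of intercept and slope. Further runs with a 0.5 SD shift and 100 participants gave about 27-93% significance for the slope-only test on shifts that fade toward baseline, against 98-100% for the joint test. When change truly builds linearly from zero, the order reverses: 87% for the joint test against 93% for slope-only, with windows of 2-10 days.

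**The case against.** The best defence is that the hypothesis concerns change with illness, not a rate after onset (protocol 9.1, SAP 5.1). Several points stand.

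- **The test is valid.** A reader might infer that a significant result for a flat shift is a false positive. It is not: the feature has changed, the test holds its size when nothing changes (9.8%), and a joint test would also send that feature to the sigmoid model.
- **The SAP does not call this slope growth.** *Growth Rate* is a separate participant-level measure, the maximum change divided by Tmax.
- **Between features, windows largely agree.** A reader might infer that slopes cannot be compared across features because their windows differ. Recovery is set by the total symptom score, so each participant has one window for all features, apart from missing recordings.
- **Falling features are not always flagged.** Near-certain significance needs a mild decline. For shifts that fade toward baseline the rate varied widely, and a feature that dropped well below baseline could give a negative slope.
- **The constraint has a rationale.** The sigmoid model also starts at zero on day 0, and windows with only two days of data make random intercepts plus slopes fragile.

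By-day summaries and mean/SD plots are planned and would show a plateau or decline. The study is also exploratory, with no decision rules. These help a reader but change neither the reported coefficient nor the gate. The per-virus analyses are optional and no formal comparison is specified, but separate slopes reported by virus invite one.

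**Conclusion.** The point holds as one about what the coefficient estimates and about the gate. The slope and its 90% CI are not a rate of progression. The dependence on window length, and the wrong sign for a linear fall to zero, are algebra and need no assumptions. The total symptom score is the endpoint least suited to the constraint, because its onset rule guarantees a day-1 jump. The p-value stands as a test of no change from baseline.

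The loss of power at the gate (about 27-93% against 98-100%) rests on an assumed 0.5 SD shift, 100 participants and fading shapes. It does not apply to a persistent shift, and it reverses slightly for linear growth from zero. The change should be made, since it is cheap and concerns the main primary-endpoint estimate.

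**What to change.** In SAP 5.2.2.3:

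1. Fit change from baseline on an intercept plus (day-1) as fixed effects, with random intercept and random slope. Pre-specify a fallback to random intercept only if the model does not converge.
2. Report the onset-day change and the daily slope separately, each with its 90% CI.
3. Gate the sigmoid model on the joint 2-df test of intercept and slope at p<0.10.
4. The slope-only model may stay as a supplementary test of any change, with a statement that its coefficient is not a daily rate.

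Bring SAP 6.1.1.1 into line. The cost is wording, one extra fixed and one extra random effect, possible use of the fallback for some features, and slightly lower power when change truly builds linearly from zero. The SAP already fits a fixed and random intercept and slope in its logit-transformed model, so the structure is not new to the plan.
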